### **3. Background and significance:**

Over the last 20 years, opioid use disorder and related deaths have risen to epidemic proportions in the United States. Unfortunately, data suggests that long-term opioid use often begins from a discharge prescription intended to treat acute surgical pain. Additionally, opioid consumption during hospitalization is associated with adverse outcomes, including respiratory arrest, delirium, bowel ileus, nausea, and prolonged length of stay.

In efforts to decrease opioid exposure after surgery, medical providers at Vanderbilt University Medical Center (VUMC) employ a multi-modal approach to pain control, which includes strategic combinations of non-narcotic pain medications and regional nerve blocks. This intentional practice, termed 'enhanced recovery pathway', has been extremely successful over the last few years, with internal data showing significant reductions in opioid consumption, improved surgical outcomes, and earlier discharges from the hospital. Our results are consistent with experiences from other enhanced recovery programs.

Evidence is clear that combinations of non-narcotic pain medications with different mechanisms of actions are synergistically effective. What is not known, however, is the individual contribution of each medication to the overall efficacy of the regimen. Thus, we aim to perform a series of randomized, controlled trials in which we systematically isolate each component of our bundled pathway.

We propose to conduct a randomized controlled trial to investigate the weight of ketamine, within a the construct of a pre-established enhanced recovery program, on a) length of stay, b) total inpatient opioid consumption, and c) surgical outcomes after major abdominal surgery. Eligible patients in our enhanced recovery program will be randomized to receive either ketamine or saline during the perioperative period, with

the remainder of the multimodal analgesic regimen consistent between the groups. Breakthrough pain will be addressed pragmatically, in accordance with suggested pathway guidelines and routine practice of our physicians.

#### **4. Rationale, specific aim(s), and hypotheses:**

AIMS: Examine the effects of ketamine, within the constructs of a multimodal pain regimen, on a) length of stay, b) opioid consumption, and c) surgical outcomes after major abdominal surgery.

**4.1 Primary Outcome:** total length of hospital stay (days). LOS is defined as the time between anesthesia beginning and the patient being discharged.

**4.2 Secondary Outcomes:**

- a) total consumption of inpatient opioids in morphine milligram equivalents
- b) surgical outcomes including rapid response, transfer to icu, and ileus
- c) the incidence of side effects, including hallucinations, sedation, adverse reactions requiring early cessation

**4.3 Exploratory Outcomes**

- a) Instances of reoperation within the index encounter
- b) Hospital readmissions to VUMC within 30 days post-discharge

**4.4 Primary Hypothesis:** Utilization of ketamine as part of a perioperative multimodal pain regimen will result in a significant reduction in length of stay as defined as the time between anesthesia beginning and the patient being discharged.

#### **5. Preliminary results including animal studies and previous human studies (if applicable):**

Ketamine has been used as a core intraoperative component of several VUMC enhanced recovery pathways since we adopted the practice. As evidence of its safety and utility became more available, we expanded its use to include the postoperative period as well (2016 consensus guidelines).

To date, no study has looked at the contribution of ketamine within an established enhanced recovery pathway. However, studies looking at perioperative ketamine infusions individually are summarized below:

PMID: 30113350: 129 patients either "opioid tolerant" or "naiive." Were randomized to Ketamine 0.12 mg/kg/h x 24 hours or a saline placebo. The primary outcome was opioid consumption during the first 24 h postoperatively. The secondary outcome was numerical pain scores during the first 24 h and central

nervous system side effects. Postoperative hydromorphone consumption was significantly reduced in the opioid-tolerant ketamine group, compared with the opioid-tolerant placebo group [0.007 (95% CI 0.006 to 0.008) versus 0.011 (95% CI 0.010 to 0.011) mg kg h, Bonferroni corrected  $P < 0.001$ ]. Postoperative low-dose ketamine infusion reduces opioid requirements for the first 24 h following spinal fusion surgery in opioid-tolerant, but not in opioid-naïve patients.

PMID: 26283834: Zakine et al. [49] performed a double-blinded study comparing the effectiveness of ketamine administration in two different settings with one control group which received placebo. The first ketamine group received a 0.5 mg/kg bolus perioperatively and a 2 µg/kg/min infusion thereafter for 48 hours; the second ketamine group received a 0.5 mg/kg bolus perioperatively and a 2 µg/kg/min infusion only for the duration of the surgical procedure. All of the patients were given morphine PCA. The authors found that cumulative morphine consumption was significantly lower in the group receiving the 48-hour infusion when compared to the shorter infusion and control groups. VAS scores were measured postoperatively and were significantly lower in the ketamine groups when compared to the control group. As an added effect, while all patients in the study received hydroxyzine preoperatively, the 48-hour infusion group experienced significantly less nausea than the control group (4% versus 27%, ). It is worth noting that there were no side effects of the ketamine, psychotomimetic, or otherwise.

PMID: 23814653: Hadi et al. [40] used low-dose IV ketamine as an adjunct to therapy during and after lumbar microdiscectomy surgery. Patients were divided into a control group, a group receiving 1 µg/kg/min perioperatively and a group receiving both 1 µg/kg/min perioperatively and 1 µg/kg/min postoperatively. The patients in the control group required first analgesic demand dose earlier than the ketamine groups. Total morphine consumption, visual analog scale (VAS) pain scores, and rates of nausea and vomiting were significantly lower in the group receiving both peri- and postoperative ketamine versus the control group.

PMID: 22374377: Suppa et al. [48] performed a similar study in women undergoing elective Cesarean sections, using a 0.5 mg/kg ketamine bolus 10 minutes after birth in addition to a 2 µg/kg/min IV ketamine infusion for 12 hours thereafter. Usage of ketamine reduced morphine requirements at the 4–8, 8–12, and 12–24-hour time points. The patients in the ketamine group showed reduced pain sensitivity at the T-10 dermatome, suggesting an antihyperalgesic effect. At three years after surgery, patients reported no differences in residual pain or dysesthetic symptoms.

PMID: 19923527: Remérand studied the effects of a 24-hour ketamine infusion in patients undergoing primary elective total hip arthroplasty in France. In a prospective, randomized, placebo-controlled, double-blind study of 154 patients, the group received an IV bolus of 0.5 mg/kg of study drug (either ketamine or placebo/saline) followed by an IV infusion for 24 hours at a dose of 2 mcg/kg/minute. All patients received general anesthesia, acetaminophen, ketoprofen (NSAID), and a morphine/droperidol mixture via IV PCA. The primary outcome of interest was 24-hour morphine consumption. The ketamine treatment group had a mean 24-hour morphine consumption of 14 mg versus 19 mg in the placebo group ( $P = 0.004$ ). Although statistically significant, the clinical relevance of a 5 mg decrease in IV morphine is unclear. However, on secondary analysis, the ketamine treatment group had statistically significant decreases in (1) the need for two crutches or a walking frame at Postoperative Day 30 (31% vs 56%;  $P = 0.0035$ ); (2) pain at rest from Postoperative Days 30 to 180 ( $P = 0.008$ ); and (3) persistent pain in the operative hip at rest at Postoperative Day 180 (8% vs 21%;  $P = 0.036$ ; relative risk reduction, 67%).

## 6. Inclusion/exclusion criteria:

### 6.1 Inclusion criteria:

- 18 years old or greater
- presenting for major, elective, abdominal surgery on the colorectal, ventral hernia, or surgical oncology services on a weekday

### **6.2 Exclusion criteria:**

- allergy or contraindication to ketamine
- unable or refused to receive a neuraxial or regional nerve block
- patient refusal
- direct transfer from operating room to ICU with endotracheal tube placed
- treating team elects to exclude the patient prior to study drug administration
- abortion of surgical procedure

### **7. Enrollment/randomization:**

Patients presenting for elective major abdominal surgery at VUMC are automatically screened to receive care within our enhanced recovery program. Patients are approached on the day of their surgery by a physician member of our Perioperative Medicine team, who describes our goals, multimodal pathways, and obtains consent to perform a regional nerve block. Eligible patients will be consented for inclusion in the trial during this initial encounter; patients returning for a follow up procedure that meets inclusion criteria will be reapproached for consent and rerandomized as appropriate. Consent for the trial will be included as an adaptation to our current consent form for neuraxial or regional nerve block procedures, with the addition of the following language:

“Vanderbilt University Medical Center (VUMC) is a learning healthcare system where we evaluate how well our routine treatments and interventions for pain control work after surgery and possible side effects they may produce. As part of your perioperative care, you will receive a bundled approach of different pain regimens that have been shown to work both alone and together to relieve pain. At VUMC, we are studying different aspects of our routine bundled pain regimen to determine the most effective parts and combinations.

If you are eligible for enrollment in a study about treatment of your pain, you may be assigned to one of multiple routinely used regimens to help control your pain. Upon enrollment, you will be randomized to receive either a ketamine or saline infusion. We are doing this study to understand which regimens have better pain control and fewer side effects in different patients. You will have pain medicine available as you need it regardless of the regimen used. Potential side effects of those pain medicines include confusion, sleepiness, agitation, slowing of your breathing, and changes in blood pressure. Data will be collected from your medical record to evaluate how well your pain

is controlled and whether or not you have any side effects. The risk of the study is that your data could be seen by people not part of the study. To help prevent this, data will be stored in a secure database to minimize the risk of anybody seeing your information. You can choose not to have your data be part of the study. Ultimately, the health care providers involved in your care will determine the best treatment plan for your pain, regardless of your taking part in the study or not. You do not have to take part in the study. If you decide not to take part in the study, none of your care will be changed because you opted not to take part. You can also choose to stop taking part in the study at any time. Patients can choose to opt out of taking part in the study by initialing the following statement:

I would like to opt-out of any studies evaluating how well my surgical pain regimen works. I understand that the physicians caring for me will determine the best treatment plan for my pain, and that this plan may still include the bundled pain regimen being studied. However, data from my medical record will not be used to evaluate how well the pain treatment regimen works or its side effects.

Randomization will be in cluster format, scheduled and tracked by the OR pharmacy. Patients and their medical providers will be blinded to their randomization arm. Provisions for breaking the blind include medical emergencies, adverse medication reactions, and participant or medical provider request.

A subset of patients may be readmitted for an additional surgery during the study period. In these instances, if the planned surgery meets inclusion criteria, the patient will be re-randomized and the readmission will be considered a new instance/encounter. For patients undergoing re-operation within the same encounter/admission, we will not re-randomize these patients. Instead, providers will order ketamine or not as appropriate per their clinical judgement.

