## **9. Risks:**

Ketamine is an analgesic that has been proven to reduce opioid consumption after surgery. It also has a role in reducing the development of chronic pain. Compared to opioids, ketamine has a favorable side-effect profile, including the maintenance of respiratory and cardiovascular stability. Ketamine does not act at the mu opioid receptor, and therefore is not associated with nausea, itching, constipation, and tolerance.

We have been safely utilizing perioperative ketamine VUMC for several years as part of our enhanced recovery pathways.

Ketamine is a controlled substance and is highly regulated, recorded, and tracked. Patients are evaluated daily at the bedside by our Preoperative Medicine Service, and patients are screened for side effects of ketamine on daily rounds. Nurses are trained to immediately report any suspicion of an adverse ketamine reaction to a member of our team, who is in-house 24/7.

**Adverse reactions to ketamine:** Adverse reactions and allergies to ketamine are routinely reviewed by both medical providers and pharmacy personnel prior to ordering and administering the drug. Ketamine is a controlled substance and is highly regulated, recorded, and tracked. Patients are evaluated daily at the bedside by our Preoperative Medicine Service, and patients are screened for side effects of ketamine on daily rounds. Nurses are trained to immediately report any suspicion of an adverse ketamine reaction to a member of our team, who is in-house 24/7.

**Selection of patients:** Only patients receiving care through our enhanced recovery pathway (which includes the standard administration of ketamine) will be eligible for participation.

**Ineffective pain control:** Patients with breakthrough pain will receive routine treatment guided by our preoperative protocols and discretion of medical providers.

**Breach of confidentiality:** The investigators have access to the medical data as part of their job standing. All database work will be performed on VUMC approved and password protected servers that are physically located in the VUMC computing environment and maintained by VUMC security standards. Only the PI and KSP will have access to study specific data.

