 - b. Mild side effects, but prefers discontinuation
 - c. Debilitating hallucinations
 - d. Debilitating dizziness
 - e. Hemodynamic instability
 - f. Other severe side effect

4. The incidence of ileus requiring gastric decompression as defined by orogastric or nasogastric tube placement in the postoperative period

Exploratory Outcomes

1. Instances of reoperation within the index encounter
2. VUMC hospital readmissions within 30 days post-discharge (not including ED visits)

Design Considerations

Randomization

Randomization will occur in clusters of one week. All patients in the same week will receive the same therapy (ketamine or placebo), with the selection being determined by a pre-generated random sequence.

Power and Sample Size

We anticipate the use of ketamine will reduce LOS following surgery start. To determine how long this trial will need to run to have sufficient power to detect a meaningful difference, we assumed 85% power, a type I error rate of 5%, and a 10% reduction in LOS. We estimated the within period correlation from preliminary data concerning the length of stay for major abdominal surgeries to be about 0.014. Given these assumptions, about 1514 patients would need to be included overall. An increase in sample size is necessary to accommodate for the two post-randomization exclusions that are pre-specified. We expect approximately 30 participants to be impacted by these post-randomization exclusions and will therefore increase the sample size by 30 to account for this exclusion (n=1544). Given surgical volumes, we expect 20 patients to be enrolled each week, and for the trial to last approximately 18 months.

Statistical Approach

Descriptive Analysis

We will describe the study cohort both overall and by treatment arm. To characterize the study sample, demographic and clinical data will be described. Categorical variables will be described using frequencies and proportions; continuous variables will be described using means and standard deviations as well as medians and interquartile ranges (IQR). Missingness will be recorded for each variable. To further assess the distribution of variables, graphical summaries will be displayed using graphs such as boxplots, dotplots, and/or histograms. No statistical testing will be performed to compare characteristics between groups. At a minimum, the following baseline variables will be described:

- Age (years)
- Sex assigned at birth (male, female, unknown)
- Race
 - Caucasian

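### The trial's consent wording gives data exposure as the risk of the study and calls the assigned regimens routine, which does not agree with the risks in protocol section 9 or with ketamine's standard place in the pathway

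*Protocol*

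**What the plan says.** Protocol section 7 sets out the language that is added to the existing consent form for neuraxial or regional nerve blocks. On the assignment it says that "you may be assigned to one of multiple routinely used regimens to help control your pain", and then: "Upon enrollment, you will be randomized to receive either a ketamine or saline infusion". Next comes "You will have pain medicine available as you need it regardless of the regimen used". The sentence after that lists five possible side effects of those medicines: confusion, sleepiness, agitation, slowed breathing and blood pressure changes. On risk it says: "The risk of the study is that your data could be seen by people not part of the study". No other item in the language is called a risk of the study.

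Protocol section 9 (Risks) is wider. It has separate headings for adverse reactions to ketamine, ineffective pain control and breach of confidentiality. Under ineffective pain control it says: "Patients with breakthrough pain will receive routine treatment guided by our preoperative protocols and discretion of medical providers". On who may take part it says: "Only patients receiving care through our enhanced recovery pathway (which includes the standard administration of ketamine) will be eligible for participation".

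Among the outcomes, protocol section 4.2(c) counts "the incidence of side effects, including hallucinations, sedation, adverse reactions requiring early cessation". Item 3 of the SAP's secondary outcomes records reasons for stopping the study drug early, among them "Debilitating hallucinations", debilitating dizziness and hemodynamic instability.

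**The concern.** The consent language makes a positive statement about what the risk of the study is, and that statement is narrower than the protocol's own risk section. It also presents the assignment as a choice among regimens in routine use, when one arm replaces a standard pathway component with blinded saline. This goes further than leaving out detail: a patient who takes the two sentences at face value would conclude that, apart from privacy, joining the study carries no risk of its own.

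Informed choice in a blinded, placebo-controlled trial is at stake. On the protocol's own account the replaced component matters: section 9 describes ketamine as proven to lower opioid use after surgery, and section 4.4 hypothesises a shorter stay with it. The point concerns patient protection and consistency between sections. It does not touch the estimand or the analysis.

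**Working it through.** No formula applies and the plan gives no figure to reproduce. The check sets the sections side by side.

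**Step 1. Risks.** Inputs: the risk headings in protocol section 9 and the consent language in section 7.

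| Risk type in section 9 | Called a risk of the study in the consent language? |
|---|---|
| Adverse reactions to ketamine | No |
| Ineffective pain control | No |
| Breach of confidentiality | Yes |

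One of three appears, so 3 − 1 = 2 are missing from the risk statement.

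**Step 2. Side effects.** Inputs: the effects named in protocol 4.2(c) and SAP secondary outcome item 3, and the five effects listed in the consent language.

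| Effect the trial counts | Where | Counterpart in the consent list |
|---|---|---|
| Hallucinations | 4.2(c) and SAP item 3 | None |
| Sedation | 4.2(c) | Sleepiness |
| Dizziness | SAP item 3 | None |
| Hemodynamic instability | SAP item 3 | Blood pressure changes |

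If the list is taken to cover ketamine, two of the four named effects have a lay counterpart and two do not. Hallucinations, the first effect named in 4.2(c), are among the missing.

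**Step 3. Which drugs the list refers to.** The list is attached to the pain medicines just mentioned, and the sentence immediately before it is about medicine given as needed. It also includes slowed breathing and blood pressure changes, whereas section 9 credits ketamine with respiratory and cardiovascular stability. Both facts favour reading the list as mainly about as-needed drugs. The plural leaves room to include the study regimen, so that reading cannot be excluded. On either reading the list is not tied to ketamine by name.

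**Step 4. Routine regimens.** Section 9 says the pathway includes ketamine as standard, and section 5 calls it a core intraoperative component of several pathways at the centre. A saline infusion in its place is therefore a departure from the pathway. The consent language discloses that saline is possible, but not that ketamine is the component a patient on this pathway would otherwise receive. It says that declining will not change care; it does not say that joining may.

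**The case against.** Several points on the other side have weight.

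- **The two arms are disclosed.** Every patient reads the same text, which names ketamine and saline, says that parts of the routine bundle are under study, and says the aim is to learn which regimens control pain better with fewer side effects. A reader might infer that patients are not told they may get saline. The documents do not support that. What is absent is the statement that ketamine is the usual component.
- **Side effects are listed.** A reader might infer that patients are told nothing about ketamine reactions. That is too strong: three of the five listed effects (confusion, sleepiness, agitation) could apply to ketamine on the broader reading, and sleepiness covers sedation.
- **The full consent process is not visible.** The language is added to a nerve-block form that the documents do not reproduce, and a physician describes the goals and pathways in person. What patients learn overall cannot be established. This limits the conclusion, but further information elsewhere would not make the sentence on risk agree with section 9.
- **The sentence may mean only the risk that research adds.** Since pathway patients would normally receive ketamine, its reactions might be seen as belonging to usual care. This is a fair reading for the ketamine arm. It does not cover the saline arm, where possibly less effective pain control arises from the study itself.
- **Detection of reactions does not rest on the consent text.** Section 9 describes daily screening for ketamine effects and nurses trained to report to a team in house at all hours, and the SAP takes stop reasons from what the provider documents. A reader might infer that patients cannot recognise or report reactions, that the safety data suffer, or that unwarned patients will more often withdraw or ask to be unblinded. Nothing in the documents supports these steps.

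**Conclusion.** The consent language and section 9 do not agree and should be reconciled. The risk statement covers one of the three risk types that section 9 lists. The description of the assignment as routine does not fit saline replacing a standard component. The side-effect list is not tied to ketamine and omits hallucinations and dizziness, both of which the trial counts.

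The finding is limited to the trial-specific wording printed in section 7 and does not extend to the whole consent process. The wording applies to everyone consented with it, against a planned total of 1544. Halving that total gives 1544 / 2 = 772 per arm if weeks split evenly, but this is only a headcount. It rests on an assumed split, includes the roughly 30 participants expected to be excluded after randomization, and measures no harm.

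The correction is worth making because it bears on patient protection, is cheap, and can be written from content the protocol and SAP already contain. It gives no reason to doubt the primary analysis.

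**What to change.** For patients still to be enrolled, amend two sentences of the section 7 language through the IRB.

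1. Make the risk statement match section 9: reactions to ketamine, naming the hallucinations and dizziness that the trial counts; possibly less effective pain control with saline; and loss of confidentiality.
2. Replace the phrase about routinely used regimens with a statement that the pathway normally includes ketamine and that some participants will receive saline instead.

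The new text should not mention that allocation goes by week. All patients in a week share an arm, and the protocol allows the blind to be broken on request. If participants knew of the weekly scheme, one unblinding could reveal the arm of others treated that week.

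The cost is the work of an IRB amendment and perhaps a slight fall in the consent rate. No study procedure, analysis or sample size changes. The documents do not say how many patients remained to be enrolled, so the number who would benefit cannot be stated.
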